### Proteinuria Response

Proteinuria responses are reflected by the reduction of proteinuria as measured by UPCR. Based on the proteinuria responses, the following response categories are defined by this clinical trial:

- Proteinuria Complete Response (Prot-CR): Reduction of proteinuria to less than 0.5 g/g, serum albumin within the reference range (3.5 – 5.2 g/dL) and stable eGFR (at least 80% of baseline)
- Proteinuria Partial Response (Prot-PR): Reduction by at least 50% of UPCR at a given visit compared to baseline, proteinuria below 3.0 g/g and stable eGFR (at least 80% of baseline), but not meeting Prot-CR

The following variables related to proteinuria responses are defined as follows.

Overall Proteinuria Response (OPR), defined as subjects achieving either Prot-CR or Prot-PR as a response (irrespective of start of prohibited medication or progressive disease prior to the proteinuria response).

Time to First Proteinuria Response (in months) prior to start of prohibited treatment or progression, defined as

[Date of first documented response of Prot-CR or Prot-PR (whichever is earlier) – Start of study drug + 1 day]/30.4375

Best Proteinuria Response (BPR) for a subject is defined when a subject is classified as having a Prot-CR or Prot-PR at any time during the trial but prior to start of prohibited treatment or progression. Responses for BPR are ordered as Prot-PR < Prot-CR. If a subject meets the criteria for more than one response category, the subject will be classified in the highest category.

Time to BPR (in months), defined as

[Date of BPR – Start date of study drug + 1 day]/30.4375

Duration of Proteinuria Response, defined as

[Date of death, PD or start of prohibited treatment (whichever is earlier) – Date of first documented response of Prot-CR or Prot-PR (whichever is earlier) + 1 day]/30.4375. Subjects with a response but no date of death, PD or start of prohibited treatment at the time of analysis

cut-off will be censored at the date of last response assessment. Subjects without a response of Prot-CR or Prot-PR are assigned a duration time of zero.

#### 7.13.4. Disease progression

##### Progressive Disease

Progressive Disease (PD) is defined as a decrease of eGFR by more than 30% of baseline eGFR, or increase in UPCR by more than 50% from baseline value and less than 10% decline of anti-PLA2R antibody titres compared to baseline.

##### End Stage Renal Disease

End Stage Renal Disease (ESRD) is defined as decrement in the subject's kidney function to a level at which renal replacement therapy is required to sustain life meeting one of the following criteria:

Was on dialysis therapy for more than 30 days continuously

Received a kidney transplant

A physician recommended renal replacement therapy (dialysis or transplant) and the subject refused therapy

Began dialysis and died < 30 days later

Confirmed eGFR < 10 ml/min/1.73m^2

#### 7.13.5. Start and end date for time to event variables

##### Start Date

For all efficacy "time to event" variables, the start date of study drug will be used as the start date.

##### End Date

For all efficacy "time to event" variables, the end dates are defined as follows:

Date of first documented response IPR, ICR or sICR (for immunological response)

Date of first documented Prot-CR or Prot-PR (for proteinuria response)

Date of first documented PD

Subjects not experiencing either response or PD defined above will be censored at the time of trial discontinuation, or the date of cut-off, whichever is earlier.

##### Calculation of "time to event" variables:

$$\text{Time to event (days)} = \text{End date} - \text{Start Date} + 1 \text{ day}$$

##### Censoring rules

For the analysis of time to event variables using the Kaplan-Meier method, the following censoring rules are defined.

**STATISTICAL ANALYSIS PLAN**

 MorphoSys AG  
 MOR202C103

Situation	Time to event variable	Date of event or censoring	Outcome	Censoring Reason
Ongoing and no event until data cut-off	Time to first immunological response, Time to BIR, Time to first proteinuria response, Time to BPR, Time to PD	Date of cut-off	Censored	Ongoing
Discontinued the study with no event	Time to first immunological response, Time to BIR, Time to first proteinuria response, Time to BPR, Time to PD	Date of last response assessment prior to study discontinuation	Censored	Discontinued without event
No baseline assessment for the time to event variable	Time to first immunological response, Time to BIR, Time to first proteinuria response, time to BPR, Time to PD	Date of C1D1	Censored	No baseline assessment
Subject received prohibited treatment before event	Time to first immunological response, Time to BIR, Time to proteinuria response, Time to BPR	Date of last response assessment prior to prohibited treatment	Censored	Start of prohibited treatment
Subject with progressive disease (PD) before event	Time to first immunological response, Time to BIR, Time to first proteinuria response, Time to BPR	Date of documented PD	Censored	Start of PD
No post-baseline assessment for the event variable	Time to first immunological response, Time to BIR, Time to first proteinuria response, time to BPR, Time to PD	Date of C1D1	Censored	No post-baseline assessment

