## 6.3. Determination of sample size

As this is a Phase Ib/IIa trial primarily conducted to explore safety endpoints, no formal statistical hypothesis has been established for the sample size calculation of this trial.

Three evaluable subjects will be enrolled in the safety run-in phase. These subjects can belong to either Cohort 1 or Cohort 2.

Once the safety run-in is completed successfully, additional subjects will be enrolled in Cohort 1 and Cohort 2 in parallel. Approximately 20 subjects will be enrolled in Cohort 1 and approximately 10 subjects will be enrolled in Cohort 2.

With a sample size of 20 subjects in Cohort 1, there is an 88% probability to observe at least one occurrence of a particular adverse event if the natural incidence of this adverse event in Cohort 1 is 10%.

Cohort 2 includes subjects refractory to IST with up to 2 prior lines of treatment. Thus it is expected that incidence of AEs will be higher in Cohort 2 than in Cohort 1. With a sample size of 10 subjects in Cohort 2, there is a 80% probability to observe at least one occurrence of a particular adverse event if the incidence of this adverse event is 15%.

---

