## 10. EFFICACY ANALYSIS

For the primary completion analysis, the analyses will be performed based on the visits during the safety run-in phase and treatment phase.

For the final analysis, the analyses will be performed based on all the visits during the trial.

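### If SAP section 10 governs, time-to-event curves at primary completion keep ongoing subjects at risk after EOT with no visit that can record an event; separately, SAP 7.13.5 gives two censoring dates for the same dropout

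*SAP*

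**What the plan says.** SAP 7.13.5 deals with censoring twice.

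- **The table.** It opens with "For the analysis of time to event variables using the Kaplan-Meier method, the following censoring rules are defined". The row "Ongoing and no event until data cut-off" assigns the cut-off date to time to first immunological response, time to BIR, time to first proteinuria response, time to BPR and time to PD. The row for subjects who left the study without an event assigns "Date of last response assessment prior to study discontinuation". No row names subjects who completed the study without an event.
- **The End Date paragraph above it.** Subjects with neither response nor PD "will be censored at the time of trial discontinuation, or the date of cut-off, whichever is earlier".

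Two other places decide which visits count. SAP section 10 states that for the primary completion analysis "the analyses will be performed based on the visits during the safety run-in phase and treatment phase", and that the final analysis uses every visit. SAP 8.4 describes the primary-analysis data as everything up to a cut-off at which the last subject has completed Cycle 6, without limiting it to a phase. Under Protocol 6.5 the treatment phase ends with the EOT visit.

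For duration of response, SAP 7.13.3 censors at the last response assessment.

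**The concern.** A subject should be counted as at risk only while an event could be observed and counted. Under section 10, an ongoing subject's last usable visit at primary completion is EOT, yet the table keeps that subject at risk until cut-off. The curve then shows people under observation and no events, whatever happens to them. For time to PD this looks like durable stability. For time to response it looks as if nobody responds late.

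SAP 8.2 summarises these variables by Kaplan-Meier quartiles. A median that would be reached at a follow-up visit would therefore be reported as not reached, beneath a curve that seems to cover a year.

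The disagreement between the End Date paragraph and the table is a separate matter. Two programmers could follow the SAP faithfully and assign different censoring dates to the same dropout.

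**Working it through.** **1. The plan's own figures.** The SAP states no figure for the Kaplan-Meier analyses. Its only design figures are the adverse-event probabilities in 6.3. They reproduce (1 − 0.90^20 = 87.8%, stated 88%; 1 − 0.85^10 = 80.3%, stated 80%) and are not in question.

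**2. Dates** (Protocol 6.5 to 6.7 and Table 2). The last dose is on Day 141, so EOT falls between 141 + 28 = Day 169 and 141 + 42 = Day 183. FUV is at 169 + 98 = Day 267 and EOS at about 169 + 196 = Day 365. Cut-off is about the last subject's EOT.

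**3. Who is ongoing at cut-off.** A planned trial of about 104 weeks less 58 weeks per subject leaves 46 weeks of accrual. Assuming uniform accrual, 28/46 = 61% are still in follow-up, (46 − 28)/46 = 39% have passed EOS, and (46 − 14)/46 = 70% have passed FUV. If the trial runs 130 or 156 weeks, accrual is 72 or 98 weeks and the ongoing share is 28/72 = 39% or 28/98 = 29%.

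**4. Effect on time to PD** (constant hazard h per month is an assumption). PD-free probability is S(m) = exp(−h·m), and EOT is at m = 169/30.4375 = 5.55 months. Under section 10 the EOT value is carried unchanged to month 12.

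| h per month | EOT value, carried flat | True at month 12 | Gap (points) |
|---|---|---|---|
| 1% | 94.6% | 88.7% | 5.9 |
| 2% | 89.5% | 78.7% | 10.8 |
| 3% | 84.7% | 69.8% | 14.9 |

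Simulation (30 subjects, 46-week accrual, visits on nominal days, no dropout) agrees. At month 12 the rule as written gives 94.5/89.3/84.6%. Using all visits up to cut-off with censoring at the last assessment gives 88.8/78.5/69.2%.

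**5. Effect on time to response** (assumed 40% by EOT and a further 20% by EOS, nominal days). As written, the curve reads 39.8% at Days 183, 300 and 379. With all visits to cut-off it reads 39.8, 49.6 and 59.5%, so the median is reached only in the second case. In every scenario the last event under the written rule fell by Day 183, while the curve ran to about Day 365 to 378.

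**6. Would moving only the censoring date help?** With visits on nominal days, censoring at the last treatment-phase assessment gives the same PD-free values at Day 183 as the written rule (94.5/89.4/84.6%); it only removes the tail. With EOT spread over its +14-day window it is harmful. Event-free subjects with an early EOT leave the risk set before later EOT visits record events. PD-free at Day 183 then falls to about 91%, 83 to 85% and 75 to 77% (the range reflects separate simulation runs). The true values, at m = 183/30.4375 = 6.01, are 94.2/88.7/83.5%. Response at Day 183 rises to about 66% against 40%.

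**7. The two dropout dates.** Take a subject last assessed at EOT (Day 169) who leaves just before FUV (Day 267) with no further assessment. The table censors at Day 169 and the End Date paragraph at about Day 267. The difference is up to 98 days, or 98/30.4375 = 3.2 months.

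**The case against.** The case for leaving the text alone has several parts.

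- **The censoring rule is not what flattens the curve.** This stands. The visit restriction does that; cut-off censoring only lengthens the tail. A reader might take the month-12 gaps in the table above as the error of the censoring rule. They are not: they are the error of reading a treatment-phase estimate as a 12-month one.
- **SAP 8.4 would admit follow-up visits.** If it governs, the tail is not flat by construction. Section 10 is the more specific text, but the SAP does not say which prevails.
- **The curves may not exist at primary completion.** SAP 6.4.2 promises only selected exploratory endpoints, and the relevant analysis sections are redacted. The redacted rows of Table 8-1 are all ticked for the primary analysis, which suggests such curves without proving them.
- **A reader might infer that every event-free subject is censored at cut-off.** The table does not say so. Dropouts get the last response assessment, and completers may fall under the same row because SAP 7.8 counts the EOS visit date as study discontinuation. In the simulation, 18/17/16 of 30 were at risk at month 9, but about 10/9/9 of them were completers assumed censored at EOS, which leaves about 8/8/7 ongoing.
- **The dropout conflict may be small.** Protocol 8.8.4 asks for a final evaluation at withdrawal; where that is done, the two dates nearly coincide. It cannot be relied on for subjects lost to follow-up.
- **Little depends on it.** The time-to-event results are descriptive, and the key secondary endpoint is a proportion.

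**Conclusion.** The point holds, with conditions. If section 10 governs, any time-to-event curve produced at primary completion is flat after the last EOT, for roughly 26 to 28 weeks, with ongoing subjects shown at risk. Up to EOT the estimates are sound. Someone who reads the tail at face value would overstate 12-month freedom from progression by about 6, 11 or 15 points at the assumed hazards, or miss the 20 points of late response in the response example. These sizes rest on the assumed rates and on uniform 46-week accrual; the flat tail does not.

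The documents do not support extending this to the final analysis. By then every subject has reached EOS or left early, and all visits count. Only the conflict over dropouts and the missing completer rule remain there. SAP section 2 records that the last-assessment rule for dropouts was adopted deliberately in version 3.0, so the End Date sentence was probably left behind.

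This should be corrected, but it does not threaten the trial's primary or key secondary results.

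**What to change.** 1. In SAP 7.13.5, delete the End Date sentence on censoring or make it match the table. Add a row that censors completers without an event at their last response assessment.
2. Reconcile SAP 8.4 with section 10 for time-to-event variables. Preferably, use all response assessments up to cut-off and censor ongoing subjects at the last one, as 7.13.3 already does for duration of response. Otherwise keep treatment-phase visits and stop the primary-analysis curves at the end of the EOT window (Day 183).
3. Do not change only the censoring date while keeping treatment-phase visits; step 6 of the working shows the bias near Day 183.
4. Under the preferred option, use nominal visit days or an interval-censored estimate. With actual dates spread over the visit windows, the same mechanism acts at the follow-up visits. In the response example the all-visits estimate rises to about 55% at Day 300 and 72% at Day 379, against 50% and 60% with nominal days.

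The cost is a few lines of SAP text and some programming, with no new data. Under the preferred option, the late part of the primary-analysis curve rests on the minority of subjects already past EOS. Under the alternative, the curve ends near EOT.

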#### **8.8.5. Withdrawal due to Use of Prohibited Therapy [Immunosuppressive Therapy]**

Subjects starting on prohibited IST other than MOR202 will be withdrawn from the clinical trial. If withdrawn in the treatment phase, these subjects will immediately be scheduled for their EOT visit (at least 28 days after the last MOR202 dose) and will not enter the follow-up phase.

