## STATISTICAL ANALYSIS PLAN

MorphoSys AG  
MOR202C103

- Time to First Immunological Response (in months) prior to start of prohibited treatment (see definition in section 7.13.6) or progression, defined as  
[Date of first documented response of IPR, ICR or sICR (whichever is earlier) – Start date of study drug + 1 day]/30.4375
- Best overall immunological response (BIR) is defined when a subject is classified as having a IPR, ICR, or sIRC at any time during the trial but prior to start of prohibited treatment or progression. Responses for BIR are ordered as IPR < ICR < sICR. If a subject meets the criteria for more than one response category, the subject will be classified in the highest category.
- Time to BIR (in months), defined as  
[Date of BIR – Start date of study drug + 1 day]/30.4375
- Duration of Immunological response (in months), defined as  
[Date of death, PD or start of prohibited treatment (whichever is earlier) – Date of first documented response of IPR, ICR or sICR (whichever is earlier) + 1 day]/30.4375. Subjects with a response but no date of death, PD or start of prohibited treatment at the time of analysis cut-off will be censored at the date of last response assessment. Subjects without a response of IPR, ICR or sICR are assigned a duration time of zero.

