### 8.2. Variable types and descriptive statistics

Descriptive statistics will be calculated using as reference the number of subjects in the relevant analysis population (any exception will be specified) according to the nature of the data as follows:

**Continuous variables** (e.g. age, body weight): number of non-missing observations, number of missing observations, arithmetic mean, standard deviation (StD), minimum and maximum values, quartiles (median, Q1 and Q3).

If there are less than 5 observations, only the number of non-missing observations, arithmetic mean, median, minimum and maximum will be presented.

Descriptive statistics of plasma concentrations and PK parameters will include number of observations, arithmetic mean, geometric mean, StD, median, coefficient of variation CV (%), geometric CV (%), minimum and maximum. Geometric mean and the geometric CV (%) will be derived from non-zero values. For plasma concentrations, the number of non-zero values (m) will also be reported.

**Categorical variables:** (e.g. gender) number of non-missing observations, the number of missing and the relevant percentage on the analysis population, number and relative frequencies.

In case of subcategories, the relative frequencies will be calculated on the basis of the subjects in the respective category, in this case a footnote will be added explaining the different denominators.

**Time variables (durations):** Will be summarized using arithmetic mean, StD, minimum and maximum values, median and quartiles (Q1, Q3) and will be presented in months (unless otherwise stated).

**Time to event variables:** (e.g. Time to Response) Unless otherwise stated, Kaplan Meier estimates of Q1, Median, and Q3 along with their 95% Confidence Intervals will be presented.

The majority of data obtained on the eCRF and entered into the database will be provided in separate data listings showing individual subject values. The planning and reporting of statistical analyses will be carried out as described in the CROs standard operating procedures (SOPs).

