### 10.1. Analysis of best immunological response rate

The key secondary objective in this trial is to assess the effect of MOR202 on serum anti-PLA2R antibodies in subjects with aMN in terms of best overall immunological response rate (BIRR).

The best overall immunological response (BIR) is defined as achieving any response of IPR, ICR or sICR at any time during the trial but prior to start of prohibited medication or progression based on the definitions in section 7.13.3.

The best overall immunological response rate (BIRR) is defined as the proportion of subjects with a best overall immunological response. The denominator will be the total number of subjects included in the analysis population.

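### Kaplan-Meier time-to-response analyses censor subjects at prohibited treatment or progression, after which no response can count, so the reported quartiles can look too favourable

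*SAP*

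**What the plan says.** SAP 7.13.5 introduces its table with "For the analysis of time to event variables using the Kaplan-Meier method, the following censoring rules are defined". Two rows matter here:

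- Prohibited treatment before the event: censored at the "Date of last response assessment prior to prohibited treatment".
- "Subject with progressive disease (PD) before event": censored at the "Date of documented PD".

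Both rows apply to the two immunological and the two proteinuria time-to-response variables. SAP 8.2 sets the default output: "Kaplan Meier estimates of Q1, Median, and Q3 along with their 95% Confidence Intervals will be presented".

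SAP 7.13.3 counts a BIR only if it occurs "at any time during the trial but prior to start of prohibited treatment or progression". It puts the same limit on BPR and on both time-to-first-response variables. SAP 10.1 says of BIRR: "The denominator will be the total number of subjects included in the analysis population". Subjects who fail before responding therefore stay in that denominator, tabulated as PD or as non-responders.

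Protocol 8.8.5 adds: "Subjects starting on prohibited IST other than MOR202 will be withdrawn from the clinical trial". Protocol 8.8.2 makes progression a reason for permanent discontinuation of MOR202.

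**The concern.** Kaplan-Meier censoring assumes that a censored subject could still have the event later, at the rate seen in those who remain under observation. That does not hold here. Once prohibited treatment has started or progression is documented, the SAP's own definitions rule out a countable response. These are competing events, and removing such subjects from the risk set passes their share to the subjects still doing well.

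The SAP handles the same events differently elsewhere. BIRR keeps these subjects as failures, and duration of response treats progression and start of prohibited treatment as end events. Only the time-to-response variables censor them.

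At stake are the reported Kaplan-Meier quartiles, and any response probability taken from the same estimate. They can be too early or too high relative to BIRR for the immunological variables, or to the proportion with a BPR for the proteinuria variables. Overall proteinuria response (OPR) is not the right comparator, because SAP 7.13.3 counts it irrespective of prohibited medication or progression.

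**Working it through.** **The plan's own figures.** The documents state no figure for time to response. Their only probabilities concern adverse events (SAP 6.3), and they reproduce: 1 − 0.90^20 = 0.878 (stated 88%) and 1 − 0.85^10 = 0.803 (stated 80%). They do not bear on this point.

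**Inputs.**
- From the documents: 20 subjects in Cohort 1 and 10 in Cohort 2 (SAP 6.3); visit days from Protocol Table 2.
- Assumed, because the documents give none: the number and days of first immunological responses, and the number k and days of subjects censored for prohibited treatment or progression before response (failures).

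**Formula.** S = product over response days of (1 − d/n), with d responders and n at risk. The Kaplan-Meier response probability is 1 − S. A subject censored on a response day counts as at risk that day. The comparator is responders divided by all subjects.

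**Cohort 2: 10 subjects, responses on Days 29, 57, 113 and 169, so BIRR = 4/10 = 40%.**
- k = 0: S = 9/10 × 8/9 × 7/8 × 6/7 = 0.600; 1 − S = 40.0%.
- k = 1 (Day 29): S = 9/10 × 7/8 × 6/7 × 5/6 = 0.5625; 1 − S = 43.8%.
- k = 2 (Days 29, 57): S = 9/10 × 7/8 × 5/6 × 4/5 = 0.525; 1 − S = 47.5%.
- k = 3 (Days 29, 57, 85): S = 9/10 × 7/8 × 4/5 × 3/4 = 0.4725; 1 − S = 52.8%. The median is reported as Day 169, although 4 of 10 respond.

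**Cohort 1: 20 subjects, responses on Days 8, 15, 29 (two), 57 (two), 85, 113, 141 and 169, so BIRR = 10/20 = 50%.** Through Day 29, S = 19/20 × 18/19 × 16/18 = 0.80 in every case.
- k = 2, both on Day 29: 14 remain at risk and 6 more respond. S = 0.80 × 8/14 = 0.457; 1 − S = 54.3%.
- k = 2, Days 29 and 57: S = 0.80 × 13/15 × 8/12 = 0.462; 1 − S = 53.8%.
- k = 4, all on Day 29: S = 0.80 × 6/12 = 0.400; 1 − S = 60.0%.
- k = 4, Days 29, 57, 85 and 113: S = 0.80 × 13/15 × 11/12 × 9/10 × 6/8 = 0.429; 1 − S = 57.1%.

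**Median reported with fewer than half responding.** Drop the Day 8 response, so that 9 of 20 respond (45%), and censor three failures on Days 29, 57 and 85. S = 17/20 × 14/16 × 12/13 × 8/11 = 0.4993; 1 − S = 50.07%. The Kaplan-Meier median becomes Day 169. With the failures kept as non-responders, the final value is 45% and no median is reached.

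**Limits.** With no failures, or with four failures at Day 267 after the last response, the Cohort 1 result is 50.0% either way. The gap is never negative. If failures stay at risk to the end of follow-up and nobody else is censored early, 1 − S returns to 50% and 40% for every k.

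**Proteinuria.** On the planned schedule UPCR is not measured between baseline and C4D1 (Day 85). Responses on Days 29 or 57 are therefore impossible for those two variables. The mechanism carries over, but the sizes above do not.

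**The case against.** The strongest reply is that the consequence is limited. BIRR, the key secondary result, already counts these subjects as failures; time to response is not a primary, key secondary or secondary endpoint, and nothing is tested. All of this stands.

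The larger examples may also be pessimistic. They assume failures in 20% (4 of 20) or 30% (3 of 10), while the only anchor in the documents is about 10% premature discontinuation before the end of Week 24, for any reason (Protocol synopsis). At 10% the gap is about 4 points, less than one subject in either cohort (5 or 10 points). It is small beside Clopper-Pearson 95% intervals of about 27% to 73% for 10/20 and 12% to 74% for 4/10. The schedule also limits early progression: the UPCR route cannot be documented before Day 85 on the planned visits and also requires less than a 10% fall in titre. Antibody titres are measured at every visit from Day 8, so many first immunological responses could precede detected progression. Earlier failures would have to come from eGFR or prohibited treatment. This narrows the size without removing the mechanism.

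Part of any gap from BIRR is ordinary censoring at cut-off or discontinuation, because BIRR keeps those subjects in its denominator too. Censoring at these events could be defended as a deliberate hypothetical strategy, but the visible text states none, and it would differ from the BIR definition. The rationale in the SAP's document history is only that assessments after prohibited treatment should not feed into response. A competing-event analysis respects that equally well.

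Three stronger readings are tempting. A reader might infer that Cohort 2 is flattered most, but no document gives rates of prohibited treatment or progression by cohort; Protocol 12.5 expects more adverse events in Cohort 2, which is a different matter. A reader might infer that the cohorts can no longer be compared, but no formal comparison is planned. A reader might also infer that misleading response curves are promised. The visible text commits only to quartiles with intervals; SAP 10.3 to 10.9 is largely redacted, so what is plotted cannot be judged.

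**Conclusion.** The point holds for all four time-to-response variables. The censoring treats subjects as still able to respond when the SAP's definitions say they cannot, and the distortion, where there is one, is always favourable to the drug.

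The size rests on assumed counts and timings:
- zero if no such event precedes another subject's later response;
- about +4 points for 2 of 20 at a BIRR of 50%, or 1 of 10 at a BIRR of 40%;
- about +7 to +10 points for 4 of 20, and about +13 for 3 of 10.

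With cohorts this small, three such subjects can decide whether a median is reported at all. BIRR is unaffected and no error rate is involved. The change should be made because the present rule conflicts with the SAP's own definition of response and no stated strategy justifies it.

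**What to change.** In SAP 7.13.5, change the prohibited-treatment row and the progression row for the four time-to-response variables in one of two ways:

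1. Treat prohibited treatment, progression and death before response as competing events, and report the Aalen-Johansen cumulative incidence with its quantiles.
2. Keep these subjects at risk as non-responders to the end of planned follow-up. This stays within the Kaplan-Meier methodology named in the Protocol synopsis.

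State that the chosen rule takes precedence over the row for study discontinuation without an event. Otherwise subjects withdrawn under Protocol 8.8.5 for starting prohibited therapy would still be censored there. Keep censoring for data cut-off and for discontinuation unrelated to these events.

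In the same edit, reconcile two statements within SAP 7.13.5. The end-date text censors subjects without an event at trial discontinuation or cut-off, whichever is earlier; the table uses the last response assessment before discontinuation.

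The cost is SAP wording and routine programming, with no new data. Option 1 departs from the Protocol's stated method and would be reported as a deviation under Protocol 12.7. The time-to-response summary may become less favourable.
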